6.1 Screening Visit

Prior to any screening procedures, informed consent will be obtained. Once consent is obtained, the following assessments will be completed and information collected for study participants within 30 days of transplant. If any screening procedure has been performed within the 30-day screening window per standard of care, results can be used for the screening visit and procedure does not need to be repeated.

- Document informed Consent
- Demographics
- Medical history
- Physical exam including vital signs and weight
- Medications
- Obtain standard of care lab results, including:
- Hematology panel-CBC and differential
- Liver Function-AST, ALT, total bilirubin
- Electrolytes
- BUN/Creatinine
- cPRA (HLA alloantibodies)
- Serum pregnancy test for women of child bearing potential

- Urine protein/creatinine except when the study subject is anuric or oliguric, and/or unable to provide a urine sample.
- Perform ECG, abnormalities must be documented as not medically relevant
- Review of medical history collected at most recent standard of care pretransplant clinic visit and primary care/specialists care visits. Determine eligibility based on inclusion/exclusion criteria

6.2 Day of Transplant (Day 0)

The first dose of investigational product will be administered on Day 0 intra-operatively. The dose of investigational product administered may not be altered. The rate of infusion may be slowed or interrupted if the subject appears to develop signs of adverse reactions or infusion-related symptoms. At later visits, these subjects may continue to be infused over a longer infusion period at the investigator's clinical discretion. The rate of infusion should not be increased above the recommended rate.

Blood pressure and heart rate will be recorded within 15 minutes prior to belimumab infusion, at 15 ± 5 minutes after the beginning of the infusion, and 15 ± 5 minutes following completion of the infusion.

Biopsy will be obtained at transplant per standard of care.

6.3 Post-Transplant Study Visits: Week 1, Week 2, Month 1, 2, 3, 4, 5, 6, 9, 12

Study visits will occur at Week 1 +/- 3 days (while in the hospital recovering from surgery), Week 2, and Months 1, 2, 3, 4, 5, 6, 9, and 12, after transplant in conjunction with standard of care. With the exception of the Week 2 visit that will take 3 hours, visits that include a belimumab infusion (Months 1, 2, 3, 4, 5) will take about 2 hours to complete. The remainder of study visits will only take about an hour. Many of the procedures required for the study are the same as those done at standard of care clinic visits and will not require additional procedures/tests. At these visits, the following procedures and tests will occur:

- Collection of vital signs (including temperature, blood pressure, heart and breathing rate, and weight), at all visits
- A brief physical exam
- Blood and urine sample collections for standard laboratory tests (all visits), except when the study subject is anuric or oliguric, and/or unable to provide a urine sample.
- Review of medications (on day of study visit.)
- Research blood sample collection at Months 1, 3, 6, 9, 12 (if consented)
- Any changes to health or medical history will be recorded and assessed

6.3.1 Study Treatment

- Belimumab: 10 mg/kg/dose will be administered IV for 6 months at the following intervals: at time of transplant (Day 0), then post -transplant at Weeks 2, 4, 8, 12, 16, and 20.

6.3.2 Study Related Clinical Assessments

- Physical examination to include patient weight and vital signs prior to each infusion and at each study visit . Physical exam will include standard neurologic assessments to monitor for the presence of any drug related toxicities as outlined in section 5.1.2.
- Adverse events recorded prior to each belimumab dose. Subjects will be asked to report any changes in sleep patterns, anxiety or mental status, suicidal ideation.
- Concomitant medications collected and reviewed at each visit

6.3.3 Laboratory Assessments

Laboratory assessments will be performed according to the schedule of events in Appendix A.

Post-transplant follow-up standard of care labs results will be collected via the Transplant Data System every month for the first year post-transplant for safety monitoring.

Subjects who do not receive a transplant, following belimumab injection, will have their labs and clinical care monitored quarterly by the study coordinators, or the PI who will collect the data from UWHC electronic records or request records from the subject's provider if not within the UWHC system.

Subjects will also have a kidney biopsy at 1 year post-transplant per standard of care.

6.3.4 Mechanistic Assessments

We will measure anti-HLA antibodies using the Single Antigen Bead Luminex assay (One Lambda, Inc., CA, USA) prior to treatment and 1, 3, 6, 9, and 12 months.

The following standard of care assays will be done and data analyzed as part of this protocol:

Single antigen Bead Luminex Antibody screening. This state of the art flow cytometry based assay is performed routinely in our HLA laboratory at the UWHC. It allows us to determine both anti HLA antibody and PRA measurements. Blood samples are analyzed for HLA antibodies by LabScreen® Single Antigen Class I and II beads LXFC kits from One Lambda, Inc (OLI, Canoga Park, CA, USA). The method is followed as described in the package insert, using 3 μ L of HLA antigen coated beads.

Kidney Transplant Biopsy: A donor biopsy will be collected intra-operatively per standard of care at the time of transplant, and percutaneously with ultrasound guidance as per standard protocol at 1 year post-transplant. Results will be collected and recorded from the electronic medical record.

6.3.5 Banking of Samples for Future Studies

If the subject agrees to allow their blood cells/plasma to be used for future research related to kidney transplantation by indicating such on the informed consent, the samples and all the coded data associated including standard of care kidney function

and study related lab results, medication and adverse event logs, and physical exam notes will be maintained by key personnel. Samples will be coded with a subject number and stored a -80° C freezer or in liquid nitrogen storage in [name] Laboratory at the University of Wisconsin Hospital and Clinics, [name]. Subjects will not be re-consented and the results of any future testing will not be provided to the subjects nor will they be used in making any clinical decisions regarding their care. The risks to the subjects are limited to breach of confidentiality and release of information to individuals not involved in this research. We will do everything possible to keep the subjects information confidential. No identifiable information will be shared. Any electronic files pertaining to health information and samples will only be accessible to the investigators and study personnel. Computers are password protected and the files will be stored on a Department of Surgery secure password protected network server. No portable electronic devices will be used for data collection or storage. No future research (with the exception of mechanistic assays identified in this protocol) or sharing of samples will be done without an IRB approved protocol.

If the subject agrees **peripheral blood will be collected prior to transplant and at 1, 3, 6, 9, and 12 months** and stored for the below future studies.

- **BAFF and APRIL measurements:** Serum BAFF and APRIL levels will be measured as described previously using the Quantikine ELISA Immunoassay (R&D Systems, Minneapolis, MN)⁽¹⁷⁾. Briefly, samples are collected in tubes without anticoagulant and spun at 2000 rpm for 10 min. Serum is collected and frozen in liquid nitrogen for long term. Standards and sera are assayed in duplicate wells. This will occur on samples prior to treatment and 1, 3, 6, 9, and 12 months.
- **B Lymphocyte Analysis:** B-cell FACS panels will be used to measure changes over the course of therapy in the transitional, naïve, memory and plasma cell compartments. For the subsets of interest, absolute numbers of cells and proportions relative to all B cells for the individual subsets will be determined, as will activation status. Specifically we will address peripheral transitional, naive, memory and plasma cell populations prior to transplant and at 1, 3, 6, 9, and 12 months post-transplant. Further exploratory analyses will include the expression of BLyS receptors (BR3, TACI and BCMA) on B cells, frequency of alloreactive B cells (using tetramers) and an analysis of the effect of belimumab on IL-10 secreting B regulatory cells. Again these assessments will be performed prior to transplant and at 1, 3, 6, 9, and 12 months post transplant
- **T Lymphocyte Analysis:** Similar assessments will be made of T cell subsets prior to transplant and at 1, 3, 6, 9, and 12 months post-transplant. Specifically we will evaluate activated T cell and T regulatory cell populations.

- **Cytokine Analysis:** Quantification of serum BLyS and APRIL levels and cytokines/chemokines associated with T-helper skewing or activation will be performed prior to transplant and at 1, 3, 6, 9, and 12, months posttransplant
- **Immunoglobulin Analysis:** Quantification of total serum levels of Immunoglobulin levels (IgM, IgA, and IgG) will be performed prior to transplant and at 1, 3, 6, 9, and 12 months post-transplant.

7. Safety Assessments

The patient will be evaluated for safety, and adverse events will be documented according to the procedures of the investigational site. The investigator will determine the relationship of the events to the administration of belimumab.

Patients will be clinically assessed for suicidal ideation and/or behavior at each visit. If patient exhibits suicidal ideations or it is verbally expressed, the PI will enter a note and refer the patient to a psychiatrist.

Expected Adverse Events (AEs) \geq Grade 2, and all unexpected adverse events will be documented, graded, and assessed for causality to belimumab by the Principal Investigator.

All Serious Adverse Events (SAEs) will be reported to GlaxoSmithKline within 24 hours. SAEs that meet the FDA and IRB reporting criteria will be reported within the specified timeframe. Serious Adverse Events will be documented, graded, and assessed for causality to belimumab by the Sponsor-Investigator.

If the patient is a WOCBP, pregnancy tests (blood; minimum sensitivity 25 IU/L of HCG) must be performed within 48 hours before the first dose and the beginning of each cycle. If the patient becomes pregnant, she must be discontinued from treatment.

Laboratory tests may be performed as part of routine standard of care as directed by subject's nephrologist. Results of these standard of care tests will be monitored as part of this study. Additional tests including a hematology profile will be done prior to each study drug cycle and hepatic function labs will be done prior to each treatment cycle for monitoring the subject's for potential drug related toxicities.

Physical exams will be performed prior to each cycle, and will include the monitoring of specific known study drug related toxicities including neuropathy and edema.

Subjects will continue to have health information collected from standard of care clinic visits, or nephrology/dialysis unit visits, and monitored for safety for 12 months from the time of discontinuation of study treatment. If subjects transplant fails prior to the 6 month time point, they will continue to have health information collected from standard of care post-transplant follow up clinic visits, or nephrology/dialysis unit visits, and monitored for safety for 12 months from the time of transplant.

MMF

Mycophenolate can cause fetal harm when administered to a pregnant female. Use of mycophenolate during pregnancy is associated with an increased risk of first trimester pregnancy loss and an increased risk of congenital malformations.

Mycophenolate affects the metabolism of oral contraceptives and may reduce their effectiveness. As such, women receiving MMF who are using oral contraceptives for birth control should employ an additional method (e.g., barrier method) resulting in two reliable forms of contraception being used simultaneously before starting study treatments, during therapy, and for 6 weeks after stopping therapy; unless abstinence is the chosen method of contraception

- For women of childbearing potential, a serum pregnancy test is required within 48 hours prior to transplant.

- For sexually active men, condoms should be used during, and for at least 90 days after cessation of mycophenolate treatment. No sperm donation should be made during this period of time. For female partners of male subjects, it is recommended to use highly effective contraception during treatment and for 90 days after the last dose of mycophenolate

- No blood donation should be made by the study subjects during mycophenolate treatment and for at least 6 weeks after stopping mycophenolate treatment

If stricter female or male contraception requirements are specified in the country-specific label for any study related therapies, they must be followed.

7.1 Adverse Events

An Adverse Event (AE) is defined as any new untoward medical occurrence or worsening of a pre-existing medical condition in a patient or clinical investigation subject administered an investigational (medicinal) product and that does not necessarily have a causal relationship with this treatment. An AE can therefore be any unfavorable and unintended sign (including an abnormal laboratory finding, for example), symptom, or disease temporally associated with the use of investigational product, whether or not considered related to the investigational product.

Adverse events are defined as any signs (including abnormal diagnostic test result) or medical diagnoses noted by medical personnel, or symptoms reported by the subject, regardless of relationship to study drug, that:

1. have onset anytime after the start of study drug treatment, or
2. increase in severity during drug treatment or procedures (pre-existing signs, symptoms or diagnoses).

Subjects will be interviewed in a non-directed manner to identify potential adverse events. This occurrence of an adverse event will be based on changes in the subject's physical examination, laboratory results, and/or signs and symptoms. Only those abnormal laboratory results that are considered clinically significant will be evaluated as a potential adverse event. All adverse events \geq Grade 2 per CTCAE, including observed or volunteered problems, complaints, or symptoms are to be recorded, if they are thought to be related to the study drug or study procedures. All documented adverse events will be monitored until they are resolved or are clearly determined to

be due to a subject's stable or chronic disease condition or intercurrent illness(es). Each adverse event is to be evaluated for duration, intensity and causal relationship with the study medication or other factors.

Adverse events will be graded according to the Common Terminology Criteria for Adverse Events (CTCAE), Version 4.0.

Grade refers to the severity of the AE. The CTCAE displays Grades 1 through 5 with unique clinical descriptions of severity for each AE based on this general guideline:

Grade 1 Mild; asymptomatic or mild symptoms; clinical or diagnostic observations only; intervention not indicated.

Grade 2 Moderate; minimal, local or noninvasive intervention indicated; limiting ageappropriate instrumental ADL.

Grade 3 Severe or medically significant but not immediately life-threatening; hospitalization or prolongation of hospitalization indicated; disabling; limiting self care ADL

Grade 4 Life-threatening consequences; urgent intervention indicated.

Grade 5 Death related to AE.

7.2 *Serious Adverse Events*

A Serious Adverse Event (SAE) is any untoward medical occurrence that at any dose:

- Is fatal
- Is life-threatening
- Requires or prolongs inpatient hospitalization
- Results in persistent or significant disability/incapacity
- Is a congenital anomaly/birth defect

The inpatient stay following the transplantation procedure will be considered SAE only if prolonged for more than 14 days.

A medical event that may not be immediately life-threatening or result in death or hospitalization but may jeopardize the subject or may require intervention to prevent a serious outcome, may also be considered serious (e.g. intensive treatment in an emergency room or at home for allergic bronchospasm; blood dyscrasias or convulsions that do not result in hospitalization; or development of drug dependency or drug abuse). Medical and scientific judgment must be exercised when classifying events as serious. The Investigator must determine both the intensity of the serious adverse event and the relationship of the event to the administration of study medications.

7.2.1 *Reporting*

It is the responsibility of the Investigator to promptly notify the Institutional Review Board of all unanticipated problems involving risk to human research subjects. All serious adverse events including fatal or life-threatening events experienced by study participants in the study will be reported to GlaxoSmithKline, Inc., to ICTR DMC, the FDA per applicable regulations, and the UW IRB according to current IRB guidelines.

Adverse Events that are:	Notify:
Serious Suspected/Related* Unexpected	GSK Medical Monitor: Within 24 hours DMC: Within 14 business days HSIRB: Within 14 business days FDA and all participating institutions as soon as possible, but no later than 15 calendar days after learning of the event
Life threatening or Fatal Suspected/Related* Unexpected	GSK Medical Monitor: Within 24 hours DMC: Within 24 hours HSIRB: Within 1 business day of learning of the event. FDA: Within 7 calendar days of learning of the event
*Events that are possibly, probably, or definitely related meet the criteria for "Suspected/Related"	

7.3 **ICTR Data Monitoring Committee (DMC)**

We plan to utilize the UW ICTR Data Monitoring Committee (DMC) to oversee the study. The UW ICTR DMC is comprised of experienced members (core plus ad hoc) with expertise required to oversee this study. The DMC members will review protocol-specific reports created by statisticians using data pulled from the ICTR OnCore clinical research management system and Research Electronic Data Capture (REDCap) data management tool. These standard reports will include an overview of study objectives, a review of actual and projected accrual rates, an evaluation of patient demographics for balance of randomization, and a summary of the number and seriousness of adverse events. An interim analysis of study results may be performed and source documents may be reviewed to allow the DMC to independently judge whether the overall integrity and conduct of the protocol remain acceptable based on data provided and reported by the Principal Investigator. The DMC will make recommendations to the Principal Investigator that could include actions of continuation, modification, suspension, or termination.

In providing oversight for the conduct of this study, the ICTR DMC will meet biannually during the study to review all adverse events. Additional meetings may be scheduled as determined by the DMC or as requested by the PI. The predefined stopping points for this study are described in section 3.6 of this protocol. We will submit all reportable events to the DMC and the Health Sciences IRB in accordance with their reporting guidelines.

8. Ethical Considerations and Compliance in Good Clinical Practice

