Accrual Objective	Kidney transplant recipients (n=5) will receive standard of care (SOC) therapy consisting of alemtuzumab and steroid induction with mycophenolic acid and tacrolimus maintenance immunosuppression, plus induction and treatment for 6 months with belimumab.

Study Design	
This is an open-label pilot-study to evaluate the safety and efficacy of belimumab plus standard of care in the prevention of de novo donor specific antibody in adult subjects after kidney transplantation.
 
We will enroll 5 adult, living donor kidney transplant recipients who are sensitized, evidenced by: Positive sum Donor Specific Antibody (DSA) <1000 MFI and/or Panel of Reactive Antibodies (PRA)>0%. The primary endpoint of this study is de novo DSA production. There are two main reasons for selecting this patient population for our proposed study. 1) Sensitized patients are known to have higher rates of de novo DSA production and 2) Patients with low levels of DSA (sum DSA<1000 MFI) will enable more fidelity in determining the DSA that is produced de novo.

Study Duration:	
Kidney transplant recipients will receive the standard of care (alemtuzumab and steroid induction with mycophenolic acid and tacrolimus maintenance immunosuppression), plus six months of therapy with belimumab. Belimumab 10 mg/kg will be administered IV for 6 months at the following intervals: Day of transplant (Day 0), and then at Weeks 2, 4, 8, 12, 16, and 20 post-transplant.
 
Subjects will be treated for 6 months with belimumab and followed for DSA production for 1 year post transplant.

Primary Study Objectives	
In this proposal we plan to determine (a) whether the addition of belimumab to the standard of care (SOC: alemtuzumab and steroid induction with mycophenolic acid and tacrolimus maintenance immunosuppression) is safe and effective in preventing de novo DSA production at 1, 3, 6, 9, and 12 months post-transplant.
 
Secondary efficacy endpoints will be 1) graft survival and function as determined by serum creatinine/eGFR and urine protein at 1, 3, 6, 9, and 12 months 2) rates of acute cellular and antibody mediated rejection, at 1, 3, 6, 9, and 12 months.

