As with all immunosuppression, administration of alemtuzumab may be associated with an increased risk of infection and the development of malignancy (especially of the skin and lymphoid system). Alemtuzumab (30 mg IV x 1) is standard induction immunosuppression for both cadaveric and living-donor renal transplants at many centers.

In 251 kidney-transplant recipients receiving alemtuzumab induction (30 mg IV x 1), the adverse events did not differ significantly between patients treated with alemtuzumab, anti-thymocyte globulin and basiliximab. The principal side effects were leucopenia (57%) and infection (32%). CMV infection occurred in 13% of the recipients and PTLD in two of the recipients.

The carcinogenic effects and the effect of alemtuzumab on fertility have not been established. Alemtuzumab is contraindicated in patients who have active acute or chronic infections that contraindicate any additional immunosuppression.

For additional information on the risks associated with alemtuzumab, refer to the package insert for Campath® (Genzyme Corporation) at the following website:
<http://www.campath.com/pdfs/2009-08-Campath%20US%20PI.pdf>

Tacrolimus: The following risks are associated with the administration of tacrolimus:

- Hypertension.
- Hyperkalemia.
- Nephrotoxicity.
- Neurotoxicity.
- Post-transplant insulin-independent diabetes mellitus.
- Myocardial hypertrophy (in most cases reversible upon dose reduction).
- Increased risk of renal insufficiency in patients with hepatic impairment.
- Increased susceptibility to infection.

For additional information on the risks of tacrolimus, refer to the Prograf® package insert at the following website: <http://www.astellas.us/docs/prograf.pdf>.

Mycophenolic Acid: The following risks are associated with the use of mycophenolic acid are:

- Increased risk of developing lymphomas, lymphoproliferative diseases and other malignancies especially of the skin in patients receiving MMF as part of an immunosuppressive regimen. The risk appears to be related to the intensity and duration of immunosuppression rather than to the use of any specific agent.
- Increased susceptibility to infection, including opportunistic infections, fatal infections and sepsis.
- Increased risk of developing latent viral infections including Progressive Multifocal Leukoencephalopathy (PML) and BK virus- associated nephropathy.

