3.2.2 Secondary Endpoints

Secondary endpoints will be 1) graft survival and function as determined by serum creatinine/eGFR and urine protein at 1, 3, 6, 9, and 12 months 2) rates of acute cellular and antibody mediated rejection at 1, 3, 6, 9, and 12 months and 3) the nature, frequency, and severity of serious and non-serious adverse events \geq Grade 2.

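### Section 7.1 admits laboratory abnormalities and Grade 2 or higher adverse events to the record only through two judgement filters that the safety endpoint and the opening of Section 7 do not contain

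*Combined protocol and SAP*

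**What the plan says.** Section 7.1 opens with two broad definitions. The first reads: "An AE can therefore be any unfavorable and unintended sign (including an abnormal laboratory finding, for example), symptom, or disease temporally associated" with use of the product, related or not. The second reads: "Adverse events are defined as any signs (including abnormal diagnostic test result) or medical diagnoses noted by medical personnel", and it adds symptoms that the subject reports, again whatever the relationship to study drug.

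Two later sentences in the same section restrict what enters the record:

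- On laboratory results: "Only those abnormal laboratory results that are considered clinically significant will be evaluated as a potential adverse event". No criterion is given, and nobody is named as judge.
- On all events of CTCAE Grade 2 or higher: they "are to be recorded, if they are thought to be related to the study drug or study procedures".

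The rest of the plan uses a different rule. The third secondary endpoint in Section 3.2.2 is "the nature, frequency, and severity of serious and non-serious adverse events" of Grade 2 or higher. The synopsis names CTCAE Version 4.0 as the scale, and Section 9 repeats the endpoint and plans descriptive statistics. The opening of Section 7 requires expected events of Grade 2 or higher, and unexpected events of any grade, to be written down, graded and then judged for causality. It makes neither clinical significance nor relatedness a condition.

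Section 9 plans no separate summary of laboratory values by grade.

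**The concern.** The endpoint is a count by grade, but Section 7.1 decides by opinion which events reach that count. A laboratory value that meets Grade 2 can be left out because someone considers it not clinically significant. Alternatively, it can be left out because it is put down to a drug other than the study drug. The second route matters here because every subject also receives alemtuzumab, tacrolimus and mycophenolic acid, which Appendix A marks as standard of care. Belimumab is marked as research.

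Safety is part of the primary objective in the synopsis. Section 1.3 acknowledges that belimumab has not previously been used together with alemtuzumab or tacrolimus. A useful safety question is therefore whether known background toxicities become more frequent or more severe. Part of the answer lies in laboratory grades. If entry depends on judgement and attribution, a low reported rate cannot be told apart from a strict entry rule. The standard committee reports in Section 7.3 summarise the number and seriousness of adverse events, so they inherit the same rule.

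**Working it through.** The plan gives no power, error rate or basis for its sample size, so there is no figure to reproduce. The check is mainly a reading of the rules against each other.

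**Step 1. One case under each rule.** Take a non-serious leukopenia that meets CTCAE Grade 2 and is attributed to alemtuzumab.

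| Rule | Enters the record? |
|---|---|
| Section 7.1, both definitions | Yes; laboratory findings count and cause is irrelevant |
| Section 7.1, laboratory sentence | Only if considered clinically significant |
| Section 7.1, relatedness sentence | No, if it is not also thought related to study drug or procedures |
| Section 7, opening | Yes; expected and Grade 2 |
| Section 3.2.2 and Section 9 endpoint | Yes; Grade 2 |

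The same result is both in and out, depending on which sentence the site follows. Removing the laboratory sentence alone would not settle it, because the relatedness sentence would still exclude this case.

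**Step 2. Is there another rule that would catch it?** Section 5.1.2 sets numeric rules for IgG and for liver chemistry. No on-study numeric rule exists for leukocytes; the lymphocyte limit in Section 4.2 applies only at entry. Serious events are covered separately, since Section 7 sends all of them to the manufacturer within 24 hours. The exposed group is therefore mainly non-serious hematology abnormalities.

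**Step 3. Illustration of size.** Inputs: n = 5 (synopsis); leukopenia in 57% of 251 alemtuzumab recipients (Section 1.3). Let f be the share of leukopenia cases that pass the entry conditions. The documents give no value for f, so the whole range is shown.

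Reported rate = 0.57 × f; expected reported count = 5 × 0.57 × f; P(none reported) = (1 − 0.57f)^5.

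| f (assumed) | Reported rate | Expected count of 5 | P(none reported) |
|---|---|---|---|
| 1 | 57% | 2.85 | 0.43^5 = 0.015 |
| 0.5 | 28.5% | 1.42 | 0.715^5 = 0.187 |
| 0.25 | 14.3% | 0.71 | 0.8575^5 = 0.464 |
| 0 | 0% | 0 | 1 |

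With f = 1 the chance of at least one case is 1 − 0.015 = 0.985. If half the cases passed each filter independently, f would be 0.5 × 0.5 = 0.25. One subject reclassified moves the observed rate by 1/5 = 20 percentage points.

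**Step 4. What n = 5 allows anyway.** Exact 95% limits are 0 to 52.2% for 0/5 and 14.7 to 94.7% for 3/5. This width comes from the sample size and not from the entry rule.

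**The case against.** The strongest reply is that a clinical-significance screen is common practice, and that the general grading guide in Section 7.1 already separates the cases: Grade 1 covers observations that need no intervention, while Grade 2 involves intervention. On that view a result of no clinical significance is Grade 1 and lies outside the endpoint. But if that is right, the screen is redundant from Grade 2 upward; if it is wrong, the screen removes events that the endpoint counts. The CTCAE laboratory cut-offs are not reproduced in the documents, so how often this would happen cannot be settled from them. The reply also leaves the relatedness sentence untouched.

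The case for limited impact largely stands. The trial is a five-subject, single-arm, descriptive pilot. Blood counts and metabolic panels are scheduled through follow-up (Appendix A), hematology and hepatic tests precede each cycle (Section 7), and monthly results are collected (Section 6.3.3). The rate could be recovered; the plan does not say that it will be.

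Three stronger readings are tempting, but the documents do not support them:

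- A reader might infer that toxicities are dropped because they are expected. Expectedness is not the stated filter, and the opening of Section 7 requires expected events of Grade 2 or higher to be documented.
- A reader might infer that ALT rises would be lost in the same way. Section 5.1.2 sets numeric thresholds, 24-hour notification and, for stopping events, a liver event form. These rules govern handling and not adverse event counting, but they leave ALT much less exposed.
- A reader might infer that the trial's leukopenia rate should be set against 57%. The plan proposes no such comparison. The figure has no grade and no stated method of ascertainment, and it concerns background alemtuzumab. Leukopenia is not among the common belimumab reactions in Section 1.3. Removing the filters would not make the two rates comparable.

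**Conclusion.** The inconsistency is real and lies in the current text. Section 7.1 applies two conditions, clinical significance and relatedness, that conflict with its own definitions, with the opening of Section 7, and with the Grade 2 endpoint in Section 3.2.2 and Section 9. Followed as written, it can undercount laboratory toxicity, with non-serious leukopenia the clearest example.

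The size cannot be estimated from the documents. The range of 0 to 2.85 expected reports among 5 subjects is an illustration. It assumes that 57% applies to this population and that f may take any value. If the source counted leukopenia of every grade, the Grade 2 or higher share can only be lower than 57%. That leukopenia is the most frequent toxicity holds for the regimen, by the rates quoted in Section 1.3, and not for belimumab itself.

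The consequence is confined to a descriptive secondary endpoint; no test or sample size is affected. The point is still worth acting on, because the correction costs little and bears on what the trial can say about the safety of a combination with no prior use.

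**What to change.** **Section 9.** Add a descriptive table or per-subject listing in which scheduled hematology and chemistry results are graded by CTCAE v4.0 directly from the laboratory values, wherever a grade exists and whether or not an adverse event was reported. Show the worst post-baseline grade per subject and the shift from baseline, with baseline taken before transplant. Creatinine already has its own secondary endpoint and need not be repeated. This table bypasses both filters.

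**Section 7.1.** Reconcile the section with the opening of Section 7. Make clinical significance and causality fields recorded for each event, so that neither is a condition for recording an event of Grade 2 or higher. State who makes each judgement. Changing only the laboratory sentence would leave the relatedness condition in force.

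Whether every Grade 2 laboratory value should also count as an adverse event is more debatable. The Section 9 table gives the laboratory picture either way.

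**Cost.** One extra table from data already scheduled and a short edit to Section 7.1. The reported rate of laboratory abnormalities will be higher. No treatment or monitoring rule changes.
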